**4.3.1.1.2 Maximum Overall Intensity**

Maximum overall intensity is derived from the daily intensities computed as described above and is calculated as the maximum of the daily intensities over the period considered.

The Grade of intensity is applied following the rules described in the Section 4.3.1.1.1.

**4.3.1.1.3 Presence**

Presence is derived from the maximum overall intensity on the period considered:

- None: No presence
- Grade 1, Grade 2, or Grade 3: Presence
- Missing: Missing presence

**450 – Quadrivalent Influenza Vaccine**

---

Subjects with at least one non-missing presence for a specific endpoint will be included in the analysis. Conversely, those without a non-missing presence will not be included in the analysis of the endpoint.

**4.3.1.1.4 Time of Onset**

Time of onset is derived from the daily intensities computed as described in Section 4.3.1.1.1. It corresponds to the first day with intensity of Grade 1, Grade 2, or Grade 3.

Note: If a reaction is not continuous (i.e., reaction occurs over two separate periods of time intervened by at least one daily intensity Missing or None) then the time of onset is the first day of the first occurrence.

Time of onset will be categorized and presented as periods of D0 to D3 and D4 to D7.

**4.3.1.1.5 Number of Days of Occurrence**

Number of days of occurrence over the period considered is derived from the daily intensities computed as described in Section 4.3.1.1.1. It corresponds to the number of days with daily intensities of Grade 1, Grade 2, or Grade 3. Number of days of occurrence on the solicited period with a specified intensity may also be derived.

For injection site and systemic reactions during the solicited period, number of days of occurrence will be displayed by periods as 1-3 days, 4-7 days, and 8 days.

**4.3.1.1.6 Overall Number of Days of Occurrence**

If a reaction is ongoing at the end of the solicited period, then the overall number of days of occurrence is derived from the daily intensities and the stop date of the reaction after the end of the solicited period. The overall number of days of occurrence is:

$(\text{stop date} - \text{last vaccination date}) + (\text{number of days of occurrence within the solicited period}) - \text{length of the solicited period} + 1$

If the stop date is missing or incomplete (contains missing data [MD]), the overall number of days of occurrence will be considered as Missing.

For injection site and systemic reactions, overall number of days of occurrence will be displayed by periods as 1-3 days, 4-7 days, 8 days, and Missing.

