### 4.3 Derived Endpoints: Calculation Methods

Terms used in the clinical safety tables to describe the safety events are specified below.

AE: adverse event includes immediate, solicited, and unsolicited non-serious or serious event.

AR: adverse reaction corresponds to related AE.

Immediate AE/AR: unsolicited non-serious systemic AE ticked "immediate (within 30 minutes from the vaccination)" by the Investigator in the eCRF or electronic serious adverse event (eSAE) with time to onset within 30 minutes after vaccination with either dose 1 or dose 2.

SR: solicited reactions are events pre-listed in the eCRF, and which occurred during the solicited period (D0 through D7 after vaccination with either dose 1 or dose 2).

Unsolicited AE: AE recorded in the eCRF unsolicited form and eSAE, excluding SRs. Therefore, include immediate AEs.

Unsolicited non-serious injection site reactions are always recorded without relationship and analyzed as ARs.

Unsolicited AEs to be analyzed are AEs which occur between Visit 1 and Visit 2 (and between Visit 2 and Visit 3 for subjects requiring two doses). Unsolicited AEs occurring after the last visit - and which are not SAE - will be presented in separate listings.

SAE: unsolicited AE considered serious by the Investigator.

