**4.3.1.2.5 Duration**

Duration is derived from the start and stop dates of the unsolicited non-serious AE provided in the clinical database:

stop date of unsolicited non-serious AE - start date of unsolicited non-serious AE + 1.

The duration should be considered as missing only if one or both of the start and stop dates of the unsolicited non-serious AE is missing or partially missing.

Duration will be displayed by period as following:

1-3 days

4-7 days

$\geq$  8 days

Missing

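### The display categories for the overall duration of solicited reactions stop at exactly 8 days, so a reaction lasting 9 days or more has no row

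*SAP*

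**What the plan says.** Section 4.3.1.1.6 begins "If a reaction is ongoing at the end of the solicited period, then the overall number of days of occurrence is derived from" two sources: the daily intensities, and a stop date falling after the solicited period. The formula takes the stop date minus the last vaccination date, adds the "number of days of occurrence within the solicited period", subtracts the length of that period, and adds 1.

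Two display rules follow in the same section. The first reserves one row for unknown values: "If the stop date is missing or incomplete (contains missing data [MD]), the overall number of days of occurrence will be considered as Missing". The second lists all the rows: "overall number of days of occurrence will be displayed by periods as 1-3 days, 4-7 days, 8 days, and Missing".

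Two neighbouring sections give a comparison:

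- Section 4.3.1.1.5 covers days within the solicited period only. There the "number of days of occurrence will be displayed by periods as 1-3 days, 4-7 days, and 8 days".
- Section 4.3.1.2.5 covers the duration of unsolicited non-serious events, which has no upper limit. Its rows are 1 to 3 days, 4 to 7 days, 8 days or more, and Missing.

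**The concern.** The variable in 4.3.1.1.6 exists to count days beyond D7, but it is displayed with rows suited to a count that cannot go beyond D7. A known duration of 9 days or more belongs to none of them.

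Programmed literally, such reactions either disappear from the duration table or leave its rows short of the number of subjects with the reaction. Otherwise someone must choose a row that the SAP does not define, possibly after seeing the data. The records at risk are not a random subset: they are the most persistent reactions. If they were dropped, the table would read as though nothing lasted longer than 8 days.

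Safety is one of the trial's two objectives (section 2.2), and section 4.2.2 names both duration and number of days of occurrence among the descriptors. Section 4.2.3.2 has the diary items followed until resolution, so the plan collects the information that this display has no place for.

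**Working it through.** **Inputs**

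- Length of the solicited period: section 4.3 describes solicited reactions as events "which occurred during the solicited period (D0 through D7 after vaccination with either dose 1 or dose 2"). D0 to D7 inclusive is 8 days.
- m: days of occurrence within D0–D7, from 1 to 8 (section 4.3.1.1.5).
- k: stop day counted from the last vaccination. Under section 4.3.1.1.7 a reaction is ongoing only if it is at least Grade 1 on the last solicited day and at least Grade 1 afterwards, so k is 8 or more and m is at least 1.
- Rows: 1–3, 4–7, 8, Missing (section 4.3.1.1.6).

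**Formula (section 4.3.1.1.6)**

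Overall days = k + m − 8 + 1

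**Is the formula itself sound?** For an unbroken reaction the result should equal stop day − start day + 1.

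| Reaction | k | m | Formula | Stop − start + 1 | Row |
|---|---|---|---|---|---|
| D0–D8 | 8 | 8 | 8 + 8 − 8 + 1 = 9 | 9 | none |
| D0–D10 | 10 | 8 | 10 + 8 − 8 + 1 = 11 | 11 | none |
| D0–D14 | 14 | 8 | 14 + 8 − 8 + 1 = 15 | 15 | none |
| D5–D12 | 12 | 3 | 12 + 3 − 8 + 1 = 8 | 8 | 8 |
| D5–D13 | 13 | 3 | 13 + 3 − 8 + 1 = 9 | 9 | none |

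The two columns agree each time, so the formula stands and only the rows are at fault.

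**Which reactions lose their row?** With m = 8 the smallest possible value for an ongoing reaction is 9 (k = 8). Every reaction present on all eight solicited days and continuing afterwards, with a known stop date, is therefore unclassifiable. With fewer days inside the period, the value first reaches 9 at a later stop day (k = 16 − m):

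| m | 8 | 7 | 6 | 5 | 4 | 3 | 2 | 1 |
|---|---|---|---|---|---|---|---|---|
| First stop day with no row | D8 | D9 | D10 | D11 | D12 | D13 | D14 | D15 |

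**How much of the range is uncovered?** Stop days D8 to D28 give 21 values; with 8 values of m that makes 21 × 8 = 168 combinations. Of these, 3 fall in 1–3 days, 18 in 4–7 days, 7 in exactly 8 days, and 140 in no row (3 + 18 + 7 + 140 = 168). This is an unweighted count of possible values. It does not predict how often they occur.

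**Comparison with the other sections.** In 4.3.1.1.5 the count cannot exceed 8, so the same rows are exhaustive there. In 4.3.1.2.5 the count is unbounded and the top row is open. Section 4.3.1.1.6 pairs an unbounded count with the closed rows.

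**The case against.** The strongest case against concerns importance. No hypothesis is tested (section 5.1.2.1), so no decision rule turns on this table. Section 5.1.2.2 lists number of days of occurrence among the solicited-reaction summaries, which reads most naturally as the D0–D7 count of 4.3.1.1.5, and that display is complete. A subject with a long reaction is still counted as having it, with its grade, onset and days within the period. The SAP also does not say that values above 8 are to be discarded; rows that fail to add up would probably be noticed when outputs are checked. Finally, the documents give no rate of reactions persisting past D7, and section 4.3.1.1.7 narrows the group: in subjects aged 12 years or older, redness or swelling that has shrunk below 25 mm after D7 does not count as ongoing.

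All of this stands, and it limits the point to one descriptive display. Understated persistence is a risk of literal programming, not an established effect. None of it supplies a row for 9 days or more, and the Missing row cannot hold a known duration without contradicting its own rule.

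A greater-than-or-equal sign could have been lost from the text as read. That is unlikely: such signs survive in sections 4.3.1.1.7, 4.3.1.2.4 and 4.3.1.2.5, and the wording matches 4.3.1.1.5, where no sign belongs.

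**Conclusion.** The concern holds. As written, the rows in section 4.3.1.1.6 do not cover the values that its own formula produces. Any solicited reaction with an overall duration of 9 days or more has no row, and that includes every reaction present throughout D0–D7 and ongoing afterwards with a complete stop date. The likely origin is a carry-over of the row labels from 4.3.1.1.5.

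The conclusion rests on an 8-day solicited period, the SAP's definition of ongoing, and the formula as printed. The number of subjects affected cannot be estimated from the document. The other displays of solicited reactions, the sample size and the immunogenicity analysis are untouched.

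**What to change.** In section 4.3.1.1.6, change the rows in one of two ways:

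- **1–3 days, 4–7 days, 8 days, > 8 days, Missing.** This is preferable because it shows reactions lasting longer than the whole solicited period as a separate row.
- **1–3 days, 4–7 days, ≥ 8 days, Missing.** This is the smaller edit and matches 4.3.1.2.5, but it pools durations of exactly 8 days with longer ones.

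Either set is exhaustive: the smallest value for an ongoing reaction is 8 + 1 − 8 + 1 = 2, and the top row becomes open. Section 4.3.1.1.5 needs no change. The cost is one altered label or one added row in the SAP and the table shell, with no new data and no change to the derivation. It is best made before the tables are programmed.

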**4.3.1.1.7 Ongoing**

Ongoing is derived from the last daily intensity of the solicited period computed as described in Section 4.3.1.1.1 and the maximum intensity on the ongoing period. The investigator's ongoing flag is not used because the measurement will determine the ongoing status of the reaction.

Note: a reaction could be derived as not ongoing for the analysis despite being considered as ongoing by the investigator (e.g., when the maximum measurement after D7 for subjects aged  $\geq 12$  years is  $> 0$  mm but  $< 25$  mm).

**450 – Quadrivalent Influenza Vaccine**

---

If the last daily intensity of the solicited period is at least Grade 1 and maximum intensity on the ongoing period is also at least Grade 1, then the reaction is considered ongoing. In any other cases the reaction will not be considered as ongoing.

**4.3.1.2 Unsolicited Non-serious AEs****4.3.1.2.1 Presence**

An observation will be considered an event if it has at least a verbatim term and is not a Grade 0 intensity event. Grade 0 events should be included in the listing “Unsolicited non-serious adverse events not included in the safety analysis.”

**4.3.1.2.2 Intensity**

Intensity for unsolicited non-serious AE will be derived according to the following classification: None, Grade 1, Grade 2, Grade 3, or Missing.

If the unsolicited non-serious AE is measurable and its preferred term is part of the list of solicited reactions, then the measurement is derived based upon and following the same rule than the intensity scales defined in the in Section 4.3.1.1.1 for that measurable injection site or systemic reaction. Note the intensity could be considered “None” (not a reaction) in the analysis despite being considered a reaction by the investigator (e.g., measurement for subjects aged  $\geq 12$  years is  $> 0$  mm but  $< 25$  mm).

Intensity for the other unsolicited non-serious AEs will correspond to the value reported in the eCRF.

The maximum intensity corresponds to the highest intensity for a unique term.

**4.3.1.2.3 Last Vaccination**

For subjects aged 6 months to 8 years:

Last vaccination before an unsolicited non-serious AE is derived from the visit numbers provided in the clinical database and is calculated as follows:

If an unsolicited non-serious AE has a non-missing visit number, the visit number should be used to determine the last vaccination before the unsolicited non-serious AE

If the visit number is missing, then the start date should be used to determine the last vaccination before the unsolicited non-serious AE

For subjects aged 9 years or older:

Last vaccination before any unsolicited non-serious AE is the study vaccination at V01.

**4.3.1.2.4 Time of Onset**

Time of onset is derived from the start date of the unsolicited non-serious AE provided in the clinical database and the date of last vaccination:

**450 – Quadrivalent Influenza Vaccine**

---

- start date of the unsolicited non-serious AE – date of last vaccination

The time of onset should be considered as missing only if one or both of the dates are missing or partially missing.

The unsolicited non-serious AEs analyzed “Within 28 days” correspond to AEs with a time of onset between 0 and 28 days after vaccination or missing. An AE with missing time of onset will be considered having occurred just after the last vaccination, so will be included in these tables.

Note: Unsolicited non-serious AE that occur before vaccination (negative time of onset) or with a time of onset higher than 28 days will not be included in analysis but will be listed separately.

Time of onset will be displayed as follows:

- D0-D3
- D4-D7
- $\geq$  D8
- Missing

**4.3.1.2.5 Duration**

Duration is derived from the start and stop dates of the unsolicited non-serious AE provided in the clinical database:

stop date of unsolicited non-serious AE - start date of unsolicited non-serious AE + 1.

The duration should be considered as missing only if one or both of the start and stop dates of the unsolicited non-serious AE is missing or partially missing.

Duration will be displayed by period as following:

1-3 days

4-7 days

$\geq$  8 days

Missing

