### ***Blood sampling***

All subjects will provide a pre-vaccination baseline blood sample (3 or 5 mLa) at D0 and a second blood sample (3 or 5 mLa) 28 days after the last vaccination.

---

a 3 mL for subjects aged 6 months to 11 years and 5 mL for subjects aged 12 years or older

*Collection of safety data*

Solicited reactions from D0 to D7 and non-serious unsolicited adverse events (AEs) from D0 to D28 will be collected after each vaccination.

Information on SAEs, including AESIs, will be collected throughout the study.

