**4.2.2 Safety Endpoints**

The endpoints for the evaluation of safety are:

- Occurrence of unsolicited AEs reported in the 30 minutes after each / any injection
- Occurrence of solicited (prelisted in the subject diary card (DC) and CRF) injection site reactions and systemic reactions within 7 days following each / any injection
- Occurrence of unsolicited (spontaneously reported) AEs within 28 days following each / any injection
- Occurrence of SAEs (including AESIs) throughout the trial (i.e., from D0 through end of the study)

Depending on the item, endpoints described include: nature (Medical Dictionary for Regulatory Activities [MedDRA] preferred term), time of onset, duration, number of days of occurrence, Grade of severity, relationship to vaccine, whether the AE led to early termination from the study, seriousness, or outcome.

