**4.3.1.3.4 Duration**

Duration will be computed using the same methodology as for unsolicited non-serious AEs described in Section 4.3.1.2.5.

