### 5.3.2.5 Start Date and Stop Date

Missing or partially missing start dates for unsolicited AEs will remain missing and not be imputed. If either the start or stop date is missing or partially missing, the time to onset will be considered to be missing. Nevertheless unsolicited AEs with missing time to onset will be included in analyses according to the visit collected.

Missing or partially missing stop dates for AEs (solicited reactions and unsolicited AEs) will remain missing and not be imputed.

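### Unsolicited AEs and SAEs unresolved at last contact are shown with duration *Missing* even when they are known to have lasted 8 days or more

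*SAP*

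**What the plan says.** Duration is among the descriptors of the safety endpoints in SAP 4.2.2 ("time of onset, duration, number of days of occurrence, Grade of severity").

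- **Unsolicited non-serious AEs (4.3.1.2.5).** The formula is "stop date of unsolicited non-serious AE - start date of unsolicited non-serious AE + 1". On absent dates the section says: "The duration should be considered as missing only if one or both of the start and stop dates" is absent or incomplete. The display rows are 1-3 days, 4-7 days, ≥ 8 days and *Missing*.
- **SAEs (4.3.1.3.4).** "Duration will be computed using the same methodology as for unsolicited non-serious AEs described in Section 4.3.1.2.5".
- **Stop dates (5.3.2.5).** "Missing or partially missing stop dates for AEs (solicited reactions and unsolicited AEs) will remain missing and not be imputed".
- **Solicited reactions continuing after D7 (4.3.1.1.6).** "If the stop date is missing or incomplete (contains missing data [MD]), the overall number of days of occurrence will be considered as Missing". The rows here are 1-3 days, 4-7 days, 8 days and *Missing*.
- **Collection period (3.2).** "Solicited reactions from D0 to D7 and non-serious unsolicited adverse events (AEs) from D0 to D28 will be collected after each vaccination".

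An ongoing status is derived only for solicited reactions (4.3.1.1.7), and it feeds no row of a duration display. Outcome is summarised separately (4.3.1.4.3) and is not linked to the derivation of duration.

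**The concern.** A stop date can be absent for two different reasons. The date may not have been obtained, so that the duration is unknown. Or the event may still have been present when the subject was last seen, so that the duration is right-censored: its end is unknown, but a lower bound is known. The rule treats both alike.

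The second kind of missing date depends on the quantity being described, because an event is open at the last visit partly because it is long. If the lower bound already reaches 8 days, the category is settled and the rule discards it. A reader of the duration table then sees too few events of 8 days or more, and a *Missing* row in which unresolved events, SAEs included, cannot be told apart from incomplete records.

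**Working it through.** The SAP gives no figure to reproduce. The check applies its rule to an event still open at the last visit.

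**Inputs.** Duration formula and rows: 4.3.1.2.5. Last visit at D28 ± 2 days for subjects aged 9 years or older: Table 3.2. Second visit 28 ± 2 days after the first, and third visit 28 ± 2 days after the second, for the two-dose groups: Table 3.1.

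**Known minimum.** For onset on day *d* and an event still present at a last visit on day *L*, the minimum duration is *L* − *d* + 1. It reaches 8 when *d* ≤ *L* − 7.

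| Last visit *L* | Onset days with known minimum ≥ 8 |
|---|---|
| D26 | D0 to D19 |
| D28 | D0 to D21 (22 of 29 onset days, D0 to D28) |
| D30 | D0 to D23 |

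For an event after dose 1 still present at the third visit, *L* counted from dose 1 lies between 26 + 26 = 52 and 30 + 30 = 60. Even with onset on D28 the minimum is 52 − 28 + 1 = 25 days, so every onset from D0 to D28 qualifies.

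**Two events under the rule.**
- Onset D5, resolved D12: 12 − 5 + 1 = 8, shown as *≥ 8 days*.
- Onset D5, unresolved at D28: at least 28 − 5 + 1 = 24 days, shown as *Missing*.

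**Direction.** Let *N* events be tabulated, of which *k* are unresolved with a known minimum of 8 or more. With all events in the denominator, the *≥ 8 days* row is too low by *k*/*N*. With missing durations left out, the plan shows *a*/*m* instead of (*a* + *k*)/(*m* + *k*), where *a* of the *m* events with a duration reach 8 days; since *a* ≤ *m*, this cannot be too high either.

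**Illustration with assumed counts.** Take 20 events with stop dates, 5 of them lasting 8 days or more, plus *k* unresolved events with onset by D21.

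| *k* | Plan's rule | Using the known minimum |
|---|---|---|
| 1 | 5/21 = 23.8% | 6/21 = 28.6% |
| 3 | 5/23 = 21.7% | 8/23 = 34.8% |
| 5 | 5/25 = 20.0% | 10/25 = 40.0% |

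These counts are not in the SAP. They show the mechanism, not an expected size.

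**Why 4.3.1.1.6 needs other treatment.** Its variable counts days of Grade 1 or higher and allows gaps. Take a reaction graded on D0 and D7 only within the solicited period, then continuing to D10. The SAP formula gives 10 + 2 − 8 + 1 = 5 days. Elapsed time would give 10 − 0 + 1 = 11. A lower bound does exist, however: a reaction graded on all 8 days from D0 to D7 and derived as ongoing has at least 8 recorded days, yet becomes *Missing* without a full stop date.

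**The case against.** The strongest reply has four parts.

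1. **Follow-up.** The SAP does not say that an AE open at the last visit never receives a stop date. It lists last contact and termination dates separately from visit dates (4.3.4.2), and follow-up of unresolved events is ordinarily a protocol matter. This stands as a limit on how many events are affected. It does not close the gap for events still open when data collection ends.
2. **Visibility.** A reader might infer that long events are dropped from the safety analysis. The SAP does not support that. They stay in the table under *Missing*, and incidence, intensity, causality, seriousness and outcome do not depend on duration. SAEs are also described by outcome (5.1.2.2). But outcome is not cross-tabulated with duration, so the duration table remains misleading taken alone.
3. **Size.** A reader might infer a bias of so many percentage points. The SAP gives no rate of unresolved AEs, so none can be stated.
4. **Consistency with 5.3.2.5.** Using a contact date might look like imputing a stop date. It does not if it serves only as a lower bound to choose a row, and the SAP should say so. Resolving partial stop dates in a similar way comes closer to imputation and is not proposed here.

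It is also tempting to carry the elapsed-time formula over to 4.3.1.1.6. That would be wrong: the variable there counts graded days, and its display has no *≥ 8 days* row.

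**Conclusion.** The point holds for 4.3.1.2.5 and, by reference, 4.3.1.3.4. An event without a stop date because it was unresolved at last contact is put in *Missing* even when its minimum duration settles the category. The error runs one way: *≥ 8 days* can be understated, never overstated. With a D28 last visit it concerns unresolved events with onset on D0 to D21. For those with onset on D22 to D28 the category is truly undetermined.

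Two assumptions carry this: that some events are still open when follow-up ends, and that the last contact recorded the event as still present. The number of such events is not given, so the size is open. No hypothesis is tested on safety, and only a descriptive display is affected. The change is worth making before the tables are programmed, but it does not touch the main safety results. In 4.3.1.1.6 the related problem is narrower: a known minimum count of days is discarded.

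**What to change.** **4.3.1.2.5, and by reference 4.3.1.3.4.** If the outcome is not resolved and the stop date is absent, compute the minimum duration as the last date on which the event was known to be present (visit or contact) − start date + 1. Show it as *≥ 8 days (ongoing)* if it is 8 or more, and otherwise as *ongoing at last contact*. Keep *Missing* for dates that are truly unknown. The separate labels keep unresolved events distinct from resolved ones.

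**5.3.2.5.** Add that this step classifies a known minimum and imputes no stop date.

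**4.3.1.1.6.** Do not use the elapsed-time formula. Show reactions derived as ongoing under 4.3.1.1.7 without a full stop date as *ongoing, stop date unknown*, with the days of occurrence in the solicited period as the minimum.

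**Cost.** A few sentences in the SAP and a few lines of derivation code. The inputs are the start date, the outcome and the visit or last contact dates, all of which the SAP already uses. The *≥ 8 days* result becomes slightly less favourable.
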